### **4.2 INCLUSION CRITERIA**

- i. Adults undergoing planned, routine EMG needle guided BTX injection into either lateral or medial rectus muscle for the treatment of strabismus.
- ii. Patients being treated by [name]. This criterion will optimise consistency of recorded data, especially clinician's opinion of needle placement and EMG signal quality.

### **4.3 EXCLUSION CRITERIA**

Patients with Chronic progressive external ophthalmoplegia (CPEO) are excluded; a highly attenuated EMG signal is expected.

#### 4.4 WITHDRAWAL CRITERIA

Should the injection not be delivered for any reason, the participant will be withdrawn from the study.

### 5 ADVERSE EVENTS

#### 5.1 DEFINITIONS

**Adverse Event (AE):** any untoward medical occurrence in a patient or clinical study subject.

**Serious Adverse Event (SAE):** any untoward and unexpected medical occurrence or effect that:

- **Results in death**
- **Is life-threatening** – refers to an event in which the subject was at risk of death at the time of the event; it does not refer to an event which hypothetically might have caused death if it were more severe
- **Requires hospitalisation, or prolongation of existing inpatients' hospitalisation**
- **Results in persistent or significant disability or incapacity**
- **Is a congenital anomaly or birth defect**

Medical judgement should be exercised in deciding whether an AE is serious in other situations. Important AEs that are not immediately life-threatening or do not result in death or hospitalisation but may jeopardise the subject or may require intervention to prevent one of the other outcomes listed in the definition above, should also be considered serious.

Potential **Adverse Events:**

- i. EMG recording system interferes with existing EMG monitor used to guide the needle, preventing delivery of treatment. In this case, the EMG recording system will be immediately disconnected from the EMG monitor and the procedure resumed.

Potential **Serious Adverse Events:** none identified.

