## 1.2 RATIONALE FOR CURRENT STUDY

The rather imprecise “rain on a tin roof” identification of the EMG signal described above for what is a precise procedure – the medial and lateral rectus muscles are around 2.5 mm to 4.7 mm in diameter – will arguably negatively impact on treatment efficacy and repeatability. There may also be an increase in the likelihood of side effects such as ptosis and vertical deviation when the toxin spreads beyond the target muscle. When the needle is guided with direct observation into the muscle belly, the number of cases of ptosis is as low as 1 in 32 cases (Wan et al., 2011), suggesting the higher rates generally observed with EMG guidance are due to suboptimal positioning of the needle. Furthermore, if more toxin is used where injection takes place distal to the optimum location, the result may be an increase in antibody formation and reduced response to the toxin. It is also difficult to teach the effective use of EMG needle guidance where such descriptive interpretation is involved.

The need for improvement was confirmed during recent research of consensus needs of a group of clinicians ([name], 2016), which distilled specific needs relating to EMG needle guidance in this context. Four of these are particularly challenging and of interest for this study:

- 1) Isolating the EOM EMG signal by reducing contamination from other muscles;
- 2) Displaying the confidence that the needle is within the EOM;
- 3) Indicating the proximity of the needle to the EOM;
- 4) Providing a signal quality score.

Clinicians ranked the first two as higher priority than the third and fourth. Note that all are dependent upon learning more about the EMG signal characteristics that are affected by distance of the needle to the target muscle.

Despite the need, commercially available handheld EMG monitors of the type typically used to guide injections in this context do not appear to assist the clinician by isolating the extraocular EMG signal from interfering EMG signals, nor do they process the EMG signal to provide additional information such as confidence of location or proximity to the EOM. This presents a potential opportunity to develop the technology and deliver benefits to patients with improved treatment efficacy.

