#### 5.2 REPORTING PROCEDURES

All adverse events should be reported. Depending on the nature of the event the reporting procedures below should be followed. Any questions concerning adverse event reporting should be directed to the Chief Investigator in the first instance.

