##### 5.2.2 Serious AEs

---

V1.8, 21st November 2018

An SAE form should be completed and faxed to the Chief Investigator within 24 hours. However, hospitalisations for elective treatment of a pre-existing condition do not need reporting as SAEs.

All SAEs should be reported to the North West – GM South REC where in the opinion of the Chief Investigator, the event was:

- ‘related’, i.e. resulted from the administration of any of the research procedures; and
- ‘unexpected’, i.e. an event that is not listed in the protocol as an expected occurrence

Reports of related and unexpected SAEs should be submitted within 15 days of the Chief Investigator becoming aware of the event, using the NRES SAE form for non-IMP studies. The Chief Investigator must also notify the Sponsor of all SAEs.

Local investigators should report any SAEs as required by their Local Research Ethics Committee, Sponsor and/or Research & Development Office.

Contact details for reporting SAEs

[contact], attention [name]

Please send SAE forms to:

Medical Physics & Clinical Engineering  
Royal Liverpool Hospital  
Royal Liverpool & Broadgreen University Hospitals NHS Trust  
[name]  
[name]  
[name]  
[contact] (Mon to Fri 09.00 – 17.00)

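### Section 5.1 makes unexpectedness part of the SAE definition, which conflicts with Section 5.2.2 and leaves a serious expected event with no reporting deadline and no sponsor notification

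*Combined protocol and SAP*

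**What the plan says.** Section 5.1 gives two definitions. An adverse event is "any untoward medical occurrence in a patient or clinical study subject", with no condition on whether it was foreseen. A serious adverse event is "any untoward and unexpected medical occurrence or effect that" meets one of five criteria: death, threat to life, new or prolonged hospitalisation, lasting or significant disability, or congenital anomaly. A further paragraph lets medical judgement extend the serious category to "Important AEs that are not immediately life-threatening or do not result in death or hospitalisation but may jeopardise the subject" or may need intervention to prevent a listed outcome. The section ends with "Potential Serious Adverse Events: none identified".

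Section 5.2 opens with "All adverse events should be reported". Section 5.2.1, headed for non-serious AEs, requires such events to be recorded whether or not they were expected. Section 5.2.2 covers SAEs. It requires a form to the Chief Investigator within 24 hours and states "The Chief Investigator must also notify the Sponsor of all SAEs". It sends to the ethics committee only those SAEs that are both related to the research procedures and unexpected, within 15 days. There, and only there, the protocol explains the second term: "an event that is not listed in the protocol as an expected occurrence".

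Section 1.2, in arguing for better needle guidance, names "side effects such as ptosis and vertical deviation" as consequences of toxin spreading beyond the target muscle.

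**The concern.** Whether an event is serious and whether it was expected are separate questions, and Section 5.2.2 treats them so: all SAEs go to the Chief Investigator and sponsor, and a narrower set goes to the ethics committee. Section 5.1 merges the two questions at the point of definition. Whoever first classifies an event could then decide that it was expected, and so not an SAE, before the Chief Investigator or sponsor has seen it.

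What is at stake is oversight, not inference. Sections 8.4 and 8.6 place the clinic at Manchester Royal Eye Hospital and the sponsor in Liverpool, and follow-up runs for up to four weeks after the injection. The sponsor therefore depends on the reporting rules to learn of a serious event in that interval.

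**Working it through.** No arithmetic applies and the plan gives no figure to reproduce. The check is to trace the definition through each reporting rule.

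**Inputs.** Let S mean that an event meets a seriousness criterion, U that it is unexpected, and R that it is related to the research procedures.

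- Section 5.1: SAE = S and U.
- Section 5.2.2, first duty (24-hour form): applies to SAE.
- Section 5.2.2, second duty (sponsor notification): applies to SAE.
- Section 5.2.2, ethics-committee report: SAE and R and U.
- Section 5.2.1 (record): applies to events that are not S.
- Section 5.2 (report): applies to all AEs, with no deadline and no named recipient.

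**Step 1: consistency.** Put the Section 5.1 definition into the ethics-committee rule: (S and U) and R and U = S and U and R. The second U changes nothing. The filter has a purpose only if some SAEs are expected, which Section 5.1 rules out. This assumes that the word has the same meaning in both sections.

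**Step 2: routing under the literal text.**

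- Serious and unexpected: SAE. The 24-hour form and sponsor notification apply, and the ethics committee is told within 15 days if the event is related.
- Serious and expected: fails the SAE definition, so neither the 24-hour rule nor the sponsor rule is triggered. It is not non-serious either, so Section 5.2.1 does not apply. Only the general sentence in Section 5.2 remains.
- Non-serious, expected or unexpected: recorded under Section 5.2.1.

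**Step 3: does anything else close the gap?** The medical-judgement paragraph in Section 5.1 widens seriousness to events that fall short of the listed outcomes. It does not mention expectedness, so it does not clearly bring an expected hospitalisation back into the definition.

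**Step 4: effect of removing U from the definition.** SAE becomes S. The 24-hour and sponsor duties then cover every serious event, subject to the exemption in Section 5.2.2 for elective hospitalisation for a pre-existing condition, which is untouched. The ethics-committee set is S and R and U, the same as in Step 1. With one meaning of the word throughout, only the serious-and-expected group changes its handling.

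**The case against.** The strongest reply is that the affected group may be empty. Section 5.2.2 supplies a listing test for what counts as unexpected, and Section 5.1 lists no potential SAEs. The one potential AE it does list is interference between the recording system and the EMG monitor, and nothing in the text makes that serious. If the listing test governs both sections, few or no serious events would count as expected. Nearly all would meet the Section 5.1 definition, and both duties would apply. Ptosis and vertical deviation appear in the rationale, not in Section 5; they are not described there as expected for safety reporting, and nothing says that either would meet a seriousness criterion. The injection is also routine care in an observational study of 25 patients.

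Much of this stands, and it limits how often the gap could matter. It does not remove the inconsistency. Section 5.1 neither defines the word nor refers to Section 5.2.2, and the listing test is given only for ethics-committee reports. A reader who knows that Section 1.2 names side effects of the injection could treat a serious instance as expected, and the text does not clearly prevent this.

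Two stronger readings should be resisted. A reader might infer that a serious expected event drops into Section 5.2.1 and is merely recorded. That section covers non-serious AEs only, and Section 5.2 still asks for all adverse events to be reported; what is missing is the deadline and the sponsor duty. A reader might also infer that expectedness is left wholly to the investigator's judgement. Section 5.2.2 does give a test; the defect is that Section 5.1 is not tied to it.

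**Conclusion.** The point holds as an inconsistency between Sections 5.1 and 5.2.2, with a narrow gap in safety reporting as its literal consequence. A serious event judged expected would escape the 24-hour form and sponsor notification, though not the general instruction to report.

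The documents give no rate of serious events, so the number affected cannot be estimated. It is likely very small among 25 patients. It may be zero if the listing test is read into Section 5.1, and above zero only if the word there is given a looser meaning. To say that all serious expected events are excluded merely restates the definition and is not a measure of impact. The documents do not support a claim that serious events will in fact be lost. No outcome measure, sample size or analysis is affected. The correction is still worth making, because it costs almost nothing and removes a classification step that could come before oversight.

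**What to change.** In Section 5.1, delete the words "and unexpected" from the SAE definition, so that seriousness alone decides whether an event is an SAE. Keep the related-and-unexpected filter in Section 5.2.2, where it selects reports to the ethics committee, together with the listing test that explains it. Sections 5.1 and 5.2.2 then agree, and every serious event has a stated route.

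The cost is two words, handled through the amendment process in Sections 8.11 and 8.12, and at most an occasional extra SAE form.

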#### 5.2 REPORTING PROCEDURES

All adverse events should be reported. Depending on the nature of the event the reporting procedures below should be followed. Any questions concerning adverse event reporting should be directed to the Chief Investigator in the first instance.

##### 5.2.1 Non serious AEs

All such events, whether expected or not, should be recorded.

##### 5.2.2 Serious AEs

---

V1.8, 21st November 2018

An SAE form should be completed and faxed to the Chief Investigator within 24 hours. However, hospitalisations for elective treatment of a pre-existing condition do not need reporting as SAEs.

All SAEs should be reported to the North West – GM South REC where in the opinion of the Chief Investigator, the event was:

- ‘related’, i.e. resulted from the administration of any of the research procedures; and
- ‘unexpected’, i.e. an event that is not listed in the protocol as an expected occurrence

Reports of related and unexpected SAEs should be submitted within 15 days of the Chief Investigator becoming aware of the event, using the NRES SAE form for non-IMP studies. The Chief Investigator must also notify the Sponsor of all SAEs.

Local investigators should report any SAEs as required by their Local Research Ethics Committee, Sponsor and/or Research & Development Office.

Contact details for reporting SAEs

[contact], attention [name]

Please send SAE forms to:

Medical Physics & Clinical Engineering  
Royal Liverpool Hospital  
Royal Liverpool & Broadgreen University Hospitals NHS Trust  
[name]  
[name]  
[name]  
[contact] (Mon to Fri 09.00 – 17.00)

## **6 ASSESSMENT AND FOLLOW-UP**

Follow-up for each patient is as set out in the Method (Section 3.2).

## **7 STATISTICS AND DATA ANALYSIS**

EOM EMG signals will be characterised by time series analysis methods [14]:

- Plotting
- Estimation of autocorrelation function
- Estimation of spectral density (to separate short-term and seasonal effects)
- Model identification (information criteria)
- Model fit (ARMA processes)

Regression analysis techniques [15] will be employed to assess the relationships between EMG signal

---

V1.8, 21st November 2018

characteristics (to be defined) and position of needle with respect to target location in EOM.

An ordinal logistic regression model will be designed to estimate the expected value of the scores conditional on signal characteristics.

Given the expected sample size of 25 subjects, it's possible to empirically assess the maximum number of signal characteristics that can be used in the model formulation as  $1/10^{\text{th}}$  of the sample size [15], i.e. 2 parameters (assuming an even spread of the scores across the subjects).

Wald statistics and the Akaike Information Criterion will be used to assess the goodness of the fit, and discrimination and calibration measures of accuracy of the model will be estimated by bootstrap resampling.

## **8 REGULATORY AND QUALITY ISSUES**

### **8.1 SAFETY**

Risks to the patient and users of the EMG Capture System have been controlled through application of Medical Physics and Clinical Engineering's Risk Management Procedure CD1451, which complies with BS EN ISO 14971:2012 – Risk Management for Medical Devices.

### **8.2 ETHICS APPROVAL**

The Chief Investigator has obtained approval from the North West – Liverpool East Research Ethics Committee and Health Research Authority (HRA) approval. The study will be submitted to each proposed research site for Confirmation of Capacity and Capability. The study will be conducted in accordance with the recommendations for physicians involved in research on human subjects adopted by the 18th World Medical Assembly, Helsinki 1964 and later revisions.

The approving body will be kept informed as in Section 8.11.

The ethical considerations of the project are viewed as minimal for the following reasons:

- The study is non-interventional;
- There is low impact on study participants, including a small change to procedure, an additional person present during the procedure and in some cases an additional follow-up visit;
- There are no after-effects of participation;
- The participant is not required to interact for the purposes of the study.

### **8.3 CONSENT**

Before the clinic session, an orthoptist will review the patient records for eligibility to enter the study. Patients are seen by the orthoptist prior to the procedure as part of standard care. During this pre-procedure appointment, if the patient is eligible to participate in the study, the study will be explained to them and

---

V1.8, 21st November 2018

they will be invited to take part. They will be offered the Participant Information Sheet to read while they wait for the procedure, and will have at least 15 minutes to decide if they wish to take part. Before the clinical procedure, the ophthalmologist Principal Investigator will address any questions or concerns, and if they wish to take part, obtain signed consent from the participant. The Chief Investigator will securely hold a copy of the consent forms. The right of the participant to refuse to participate without giving reasons shall be respected.

After the participant has entered the study, the ophthalmologist remains free to deviate from the protocol at any stage if he feels it is in the participant's best interest, but the reasons for doing so should be recorded. In these cases, the participants remain within the study for the purposes of follow-up and data analysis.

All participants are free to withdraw at any time from the study without giving reasons and without prejudicing further treatment. If a participant withdraws their consent to take part in the study, their personally-identifiable data will be securely deleted; any anonymous data already collected will be retained.

#### **8.4 CONFIDENTIALITY**

The Chief Investigator will preserve the confidentiality of participants taking part in the study and will abide by the General Data Protection Regulation.

All patient data including identifiable audio / video recordings will be recorded directly onto an encrypted laptop drive during the clinic. After each clinic, the laptop and encrypted data stored on it will be physically transported by the Chief Investigator from Manchester Royal Eye Hospital to Royal Liverpool Hospital for processing and statistical analysis. The data will be transferred from the laptop to the local NHS computer network as soon as practicable after the clinic, and the data immediately removed from the laptop encrypted drive.

All data will be held by Medical Physics and Clinical Engineering, Royal Liverpool Hospital on secure, password protected and firewalled network facilities provided by the department. Security arrangements include nightly backups and access controls to restrict access to those who need it. Analysis will be carried out within Medical Physics and Clinical Engineering, Royal Liverpool Hospital, by the Chief Investigator ([name]) and the Statistician ([name]). Personal, identifiable data will only be used for this study, and all steps reasonably necessary will be taken to ensure such data will only be disclosed to those involved in the study that have a need in relation to this study.

Within three months of the end of the study, following analysis of the data, all personal identifiable data will be destroyed. Video recordings will be deleted, and any identifiable or pseudonymous participant identifiers will be removed. All deleted data will also be removed from any backups. The remaining anonymous data will be stored securely for three years, after which it will be destroyed; similarly, it will be removed from any backups. The anonymous data will be held for this period as it may contribute to a further, larger study if this pilot study indicates that additional research is required. This may reduce the

number of participants required in subsequent research.

The data custodian will be [name], Royal Liverpool Hospital.

#### **8.5 INDEMNITY**

This study is covered by NHS indemnity.

#### **8.6 SPONSOR**

The Royal Liverpool and Broadgreen University Hospitals NHS Trust will act as Sponsor for this study. It is recognised that as an employee of the Trust, the Chief Investigator has been delegated specific duties, as detailed in the Sponsorship Approval letter.

#### **8.7 FUNDING**

Medical Physics and Clinical Engineering, Royal Liverpool Hospital are funding direct costs and Royal Liverpool staff opportunity costs.

#### **8.8 AUDITS**

The study may be subject to inspection and audit by Royal Liverpool and Broadgreen University Hospitals NHS Trust under their remit as sponsor and other regulatory bodies to ensure adherence to GCP and the NHS Research Governance Framework for Health and Social Care (2nd edition).

#### **8.9 REGULATORY APPROVAL**

The study is not required to be registered with the MHRA as it is not a clinical investigation of a new medical device.

#### **8.10 LOCAL APPROVAL**

Local approval will be sought from Royal Liverpool Hospital and Manchester Royal Eye Hospital Research & Development departments following local procedures.

#### **8.11 COMMUNICATION PLAN**

Stakeholders will be kept informed by the Chief Investigator as follows:

Activity	Principal Investigator at Manchester Royal Eye Hospital	Royal Liverpool R&D (Sponsor)	Manchester Royal Eye Hospital R&D	Health Research Authority
Study protocol	Consult	Seek approval	Seek approval	Seek approval

V1.8, 21st November 2018

Non-substantial deviations  from protocol	Consult	Inform	Inform	Inform at end of study
Substantial deviations from protocol	There will be no intentional substantial deviations from the protocol. Substantial changes must be made by approved amendment to the protocol. Any unintentional substantial deviations will result in the study being suspended while the Ethics Committee is informed and a protocol amendment made if appropriate.			
Non-substantial changes  of any documentation already approved by the Ethics Committee	Inform	Inform	Inform	Inform
Substantial changes  (amendments) of any documentation already approved by the Ethics Committee	Consult	Seek approval	Seek approval	Seek approval
Premature ending of the study	Consult	Inform	Inform	Inform
Planned end of study	Inform	Inform	Inform	Inform
Outcome of study	Inform	Inform	Inform	Inform

